7.3. Lost to Follow-up

A participant will be considered lost to follow-up if the participant repeatedly fails to return for scheduled visits and is unable to be contacted by the study site.

The following actions must be taken if a participant fails to return to the clinic for a required study visit:

- The site must attempt to contact the participant and reschedule the missed visit as soon as possible. Counsel the participant on the importance of maintaining the assigned visit schedule and ascertain whether the participant wishes to and/or should continue in the study;
- Before a participant is deemed lost to follow-up, the investigator or designee must make every effort to regain contact with the participant (where possible, 3 telephone calls and, if necessary, a certified letter to the participant's last known mailing address or local equivalent methods). These contact attempts should be documented in the participant's medical record;
- Should the participant continue to be unreachable, the participant will be considered to have withdrawn from the study.

8. STUDY ASSESSMENTS AND PROCEDURES

8.1. Administrative and Baseline Procedures

The investigator (or an appropriate delegate at the investigator site) must obtain a signed and dated ICD before performing any study-specific procedures.

Study procedures and their timing are summarized in the SoA. Protocol waivers or exemptions are not allowed.

Adherence to the study design requirements, including those specified in the SoA, is essential and required for study conduct.

All screening evaluations must be completed and reviewed to confirm that potential participants meet all eligibility criteria. The investigator will maintain a screening log to record details of all participants screened and to confirm eligibility or record reasons for screening failure, as applicable.

Participants will be screened within 28 days prior to administration of the study intervention to confirm that they meet the study population criteria for the study. If the time between screening and dosing exceeds 28 days as a result of unexpected delays (eg, delayed drug shipment), then participants do not require rescreening if the laboratory results obtained prior to first dose administration meet eligibility criteria.

A participant who qualified for this protocol but did not enroll from an earlier cohort/group may be used in a subsequent cohort without rescreening, provided laboratory results obtained prior to the first dose administration meet eligibility criteria for this study. In addition, other clinical assessments or specimen collections, eg, retained research samples, may be used without repeat collection, as appropriate.

Every effort should be made to ensure that protocol-required tests and procedures are completed as described. However, it is anticipated that from time to time there may be circumstances outside the control of the investigator that make it unfeasible to perform the test. In these cases, the investigator must take all steps necessary to ensure the safety and well-being of the participant. When a protocol-required test cannot be performed, the investigator will document the reason for the missed test and any corrective and preventive actions that they have taken to ensure that required processes are adhered to as soon as possible. The study team must be informed of these incidents in a timely manner.

Safety/laboratory/analyte results that have been collected for the purposes of this study and could unblind the study will not be reported to investigative sites or other blinded personnel until the study has been unblinded.

If an IV catheter is utilized for blood sample collections, ECGs and vital sign assessments (pulse rate and BP) should be collected prior to the insertion of the catheter.

For samples being collected and shipped, detailed collection, processing, storage, and shipment instructions and contact information will be provided to the investigator site prior to initiation of the study.

The total blood sampling volume for individual participants in this study is approximately 120 mL. The actual collection times of blood sampling may change. Additional blood samples may be taken for safety assessments at times specified by Pfizer, provided the total

volume taken during the study does not exceed 550 mL during any period of 56 consecutive days.

To prepare for study participation, participants will be instructed on the information in the Lifestyle Considerations section [5.3](#) and Concomitant Therapy section [6.9](#) of the protocol.

8.1.1. Baseline Procedures

Planned timepoints for medical history and demography are provided in the [SoA](#).

8.2. Efficacy Assessments

Not applicable

8.3. Safety Assessments

Planned time points for all safety assessments are provided in the [SoA](#). Unscheduled safety measurements may be obtained at any time during the study to assess any perceived safety issues.

8.3.1. Physical Examinations

A complete physical examination will include, at a minimum, head, ears, eyes, nose, mouth, skin, heart and lung examinations, lymph nodes, and gastrointestinal, musculoskeletal, and neurological systems.

A brief physical examination will include, at a minimum, assessments of general appearance, the respiratory and cardiovascular systems, and participant-reported symptoms.

Physical examinations may be conducted by a physician, trained physician's assistant, or nurse practitioner as acceptable according to local regulation.

Height and weight will also be measured and recorded as per the [SoA](#). For measuring weight, a scale with appropriate range and resolution is used and must be placed on a stable, flat surface. Participants must remove shoes, bulky layers of clothing, and jackets so that only light clothing remains. They must also remove the contents of their pockets and remain still during measurement of weight.

Physical examination findings collected during the study will be considered source data and will not be required to be reported, unless otherwise noted. Any untoward physical examination findings that are identified during the active collection period and meet the definition of an AE or SAE ([Appendix 3](#)) must be reported according to the processes in [Sections 8.4.1 to 8.4.3](#).

8.3.2. Vital Signs

8.3.2.1. Blood Pressure and Pulse Rate

Supine BP will be measured with the participant's arm supported at the level of the heart and recorded to the nearest mm Hg after approximately 5 minutes of rest. The same arm

(preferably the dominant arm) will be used throughout the study. Participants should be instructed not to speak during measurements.

The same properly sized and calibrated BP cuff will be used to measure BP each time. The use of an automated device for measuring BP and pulse rate is acceptable; however, when done manually, pulse rate will be measured in the brachial/radial artery for at least 30 seconds. When the timing of these measurements coincides with a blood collection, BP and pulse rate should be obtained prior to the nominal time of the blood collection.

Additional collection times, or changes to collection times, of BP and pulse rate will be permitted, as necessary, to ensure appropriate collection of safety data.

Any untoward vital sign findings that are identified during the active collection period and meet the definition of an AE or SAE ([Appendix 3](#)) must be reported according to the processes in [Sections 8.4.1 to 8.4.3](#).

8.3.3. Electrocardiograms

ECG measurements must be obtained prior to vital signs assessment, blood samples, and prior to dosing (note that, where scheduled at the same nominal time, the ECG measurement time must be as close as possible to the PK sampling time). It is imperative that the order and timing of all study procedures, including meal and snack times, be approximately the same (± 15 minutes) across all study periods.

Standard 12-lead ECGs (with a 10-second rhythm strip) should be collected at times specified in the SoA section of this protocol using an ECG machine that automatically calculates the HR and measures PR interval, QT interval, QTcF, and QRS complex. All scheduled ECGs should be performed after the participant has rested quietly for at least 5 minutes in a supine position. Supine body position with fully lowered headrest should be consistently maintained for each ECG performed. Environmental distractions in the clinic (TV, radio, conversation) and other study procedures (eg, BP measurement, PK sampling) during both the pre-ECG rest and the ECG recording period must be minimized. In particular, changes in heart rate should be avoided.

Triplet 12-lead ECGs will be obtained approximately 2 minutes apart; the average of the triplicate ECG measurements collected before dose administration on Day 1 of each period will serve as each participant's baseline QTcF value. 3 baseline pre-dose measurements are needed for CQT analysis, these ECGs will be done approximately 40 min, 25 min, and 10 min before the pre-dose meal. The average of the triplicate ECGs over the 3 pre-dose measurements (total of 9 ECGs) will serve as each participant's baseline QTc value.

To ensure safety of the participants, a qualified individual at the investigator site will make comparisons to baseline measurements. Additional ECG monitoring will occur if a) the mean value from the triplicate measurements for any postdose QTcF interval is increased by ≥ 60 ms from the baseline and is > 450 ms; or b) an absolute QT value is ≥ 500 ms for any scheduled ECG. If either of these conditions occurs, then a single ECG measurement must be

repeated at least hourly until QTcF values from 2 successive ECGs fall below the threshold value that triggered the repeat measurement.

If a) a postdose QTcF interval remains ≥ 60 ms from the baseline and is > 450 ms; or b) an absolute QT value is ≥ 500 ms for any scheduled ECG for greater than 4 hours (or sooner, at the discretion of the investigator); or c) QTcF value get progressively longer, the participant should undergo continuous ECG monitoring. A cardiologist should be consulted if QTcF values do not return to less than the criteria listed above after 8 hours of monitoring (or sooner, at the discretion of the investigator).

Special attention should be given to ensure identical ECG lead placement during every measurement. In some cases, it may be appropriate to repeat abnormal ECGs to rule out improper lead placement as contributing to an observed ECG abnormality. The lead to be used for interval measurements should be pre-specified; baseline and on-treatment measurements should be using the same lead. Every attempt should be made to use the same ECG machine throughout the study for a given participant.

In this study, a semi-automated approach to ECG acquisition will be used. This technique uses a computer algorithm for the initial placement of reference marks on the waveforms to note where on the tracing the computer is making its measurements. A standard semi-automated algorithm will be used so that a limited number of CRU staff will review program-determined interval onsets and offsets and modify using digital calipers on the rare occasion when this is necessary. Where possible, the same person should review all ECG measurements for a given participant throughout the all study periods. This review must be performed by an appropriately qualified and blinded member of CRU staff. Use of this semi-automated algorithm is designed to further improve the validity of the automated ECG readout by reducing the variability associated with interpretation of the ECG waveform. This approach can have the advantage of greater consistency and reproducibility than fully manual readings, while providing an opportunity to correct any mistakes made by the algorithmic methods. Recent evidence suggests that automated techniques are capable of detecting small changes in the QTc similar to those with manual readings and with the same conclusion.¹⁰

The final ECG report should be maintained in the participant's source documentation and be the final interpretation of the ECG recording. Any clinically significant changes from the baseline/Day 1 ECG may potentially be AEs ([Appendix 8](#)) and should be evaluated further, as clinically warranted.

It is important that leads be placed in the same positions each time in order to achieve precise ECG recordings. If a machine-read QTc value is prolonged, as defined above, repeat measurements may not be necessary if a qualified medical provider's interpretation determines that the QTcF values are in the acceptable range.

ECG values of potential clinical concern are listed in [Appendix 8](#).

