9.3.1.2. ECG Data Summaries

Mean baseline and changes from baseline for QTcF, QTcB, QT (uncorrected), PR, QRS and heart rate will be calculated for each participant and summarized descriptively (N, mean, standard deviation [SD], median, minimum and maximum) by treatment and time postdose.

Placebo-corrected change from baseline for QTcF, QT (uncorrected) and heart rate differences will be summarized (N, mean, 90% CI) and plotted (mean) for each treatment and time point postdose.

Categorization of HR, QRS, and PR intervals will be described in the SAP. Categorization of maximum QTc will be provided for QTcF by treatment using the following criterion.

Absolute Maximum (msec)	<450	450 to <480	480 to <500	≥500
Maximum Increase from Baseline (msec)	<30	30 to <60	>60	

If any of the 3 individual ECG tracings has a QTcF value ≥500 msec, but the mean of the triplicates is < 500 msec, the data from the participant's individual tracing will be described in a safety section of the study report in order to place the ≥500 msec value in appropriate clinical context. However, values from individual tracings within triplicate measurements

PFIZER CONFIDENTIAL

CT02-GSOP Clinical Pharmacology Protocol Template (01 April 2022)

Page 68

that are ≥ 500 msec will not be included in the categorical analyses unless the average from the triplicate measurements is also ≥ 500 msec.

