10.8. Appendix 8: ECG Findings of Potential Clinical Concern

ECG Findings That May Qualify as AEs

Marked sinus bradycardia (rate <40 bpm) lasting minutes.New PR interval prolongation >280 ms.New prolongation of QTcF to >480 ms (absolute).New prolongation of QTcF by >60 ms from baseline.New-onset atrial flutter or fibrillation, with controlled ventricular response rate: ie, rate <120 bpm.New-onset type I second-degree (Wenckebach) AV block of >30 seconds duration.Frequent PVCs, triplets, or short intervals (<30 seconds) of consecutive ventricular complexes.
ECG Findings That May Qualify as SAEs

QTcF prolongation >500 ms.Absolute value of QTcF >450 ms AND QTcF change from baseline >60 ms.New ST-T changes suggestive of myocardial ischemia.New-onset LBBB (QRS complex >120 ms).New-onset right bundle branch block (QRS complex >120 ms).Symptomatic bradycardia.Asystole:
In awake, symptom-free participants in sinus rhythm, with documented asystolic pauses ≥ 3 seconds or any escape rate <40 bpm, or with an escape rhythm that is below the AV node.In awake, symptom-free participants with atrial fibrillation and bradycardia with 1 or more asystolic pauses of at least 5 seconds or longer.Atrial flutter or fibrillation, with rapid ventricular response rate: rapid = rate >120 bpm.

- Sustained supraventricular tachycardia (rate >120 bpm) (“sustained” = short duration with relevant symptoms or lasting >1 minute).
- Ventricular rhythms >30 seconds’ duration, including idioventricular rhythm (HR <40 bpm), accelerated idioventricular rhythm (HR >40 bpm to <100 bpm), and monomorphic/polymorphic ventricular tachycardia (HR >100 bpm [such as torsades de pointes]).
- Type II second-degree (Mobitz II) AV block.
- Complete (third-degree) heart block.

ECG Findings That Qualify as SAEs

- Change in pattern suggestive of new myocardial infarction.
- Sustained ventricular tachyarrhythmias (>30 second duration).
- Second- or third-degree AV block requiring pacemaker placement.
- Asystolic pauses requiring pacemaker placement.
- Atrial flutter or fibrillation with rapid ventricular response requiring cardioversion.
- Ventricular fibrillation/flutter.
- At the discretion of the investigator, any arrhythmia classified as an adverse experience.

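### Protocol 8.3.3 sets its 500 ms repeat-ECG trigger on uncorrected QT only, so on the literal text a triplicate-mean QTcF of 500 ms or more can start no hourly repeats when baseline QTcF is above 440 ms and heart rate is slightly above 60 bpm

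*Protocol*

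**What the plan says.** Protocol 8.3.3 lists QT and QTcF as separate outputs of the ECG machine, and then sets out the safety steps.

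- **Hourly repeats, limb (a):** the triplicate-mean QTcF is up by at least 60 ms from baseline and is above 450 ms.
- **Hourly repeats, limb (b):** "an absolute QT value is ≥ 500 ms for any scheduled ECG. If either of these conditions occurs", followed by the order for a single ECG to be "repeated at least hourly until QTcF values from 2 successive ECGs fall below the threshold value that triggered the repeat measurement".
- **Continuous monitoring:** limb (a) persists; or "an absolute QT value is ≥ 500 ms for any scheduled ECG for greater than 4 hours"; or, limb (c), QTcF lengthens progressively.
- **Cardiologist:** "A cardiologist should be consulted if QTcF values do not return to less than the criteria listed above after 8 hours of monitoring".
- **Waiver:** "If a machine-read QTc value is prolonged, as defined above, repeat measurements may not be necessary", provided that a qualified medical reader finds the QTcF acceptable.

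Other sections work in QTcF. Appendix 8 lists "QTcF prolongation >500 ms" and "Absolute value of QTcF >450 ms AND QTcF change from baseline >60 ms" among findings that may qualify as SAEs. Section 9.3.1.2 has a reporting rule that begins "If any of the 3 individual ECG tracings has a QTcF value ≥500 msec". Exclusion criterion 11 makes QTcF the deciding interval at screening. Section 7.1 uses the combined term QT/QTc: above 500 ms, or more than 60 ms over baseline, the participant must stop study treatment and be followed for safety.

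**The concern.** The rule is entered on one scale and left on another. Limb (b) is the only absolute 500 ms trigger for repeats, and as written it does not mention corrected QT. Above 60 bpm, QT is shorter than QTcF, so a QTcF of 500 ms or more can occur with QT below 500 ms. If the rise from baseline is also under 60 ms, limb (a) is silent too.

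A value that Appendix 8 treats as a possible SAE could then start no hourly repeats. If it stayed flat, it would also meet none of the three conditions for continuous monitoring. The hourly repeats are the step in 8.3.3 that gives prompt confirmation, and section 7.1 itself gives extra weight to a finding seen on more than one ECG. For a value first seen after the Day 3 morning dose, which is the last dose of the period (6.1.1), stopping treatment can affect only later periods. Monitoring is then the safeguard left within that period.

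**Working it through.** The plan states no figure for this point, so there is none to reproduce. The check applies the plan's own formula to its own limits.

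**Inputs.** Fridericia formula, QTcF = QT/RR^(1/3) with RR = 60/HR (Protocol 9.3.1.1). Limbs (a) and (b) (8.3.3). Entry limit of 450 ms on QTc (exclusion criterion 11).

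**Step 1: when limb (b) is silent.** QT = QTcF × (60/HR)^(1/3). QT is below 500 ms when HR > 60 × (QTcF/500)³.

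| QTcF (ms) | Limb (b) silent above (bpm) |
|---|---|
| 500 | 60.0 |
| 502 | 60.7 |
| 505 | 61.8 |
| 509 | 63.3 |
| 510 | 63.7 |

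**Step 2: when limb (a) is silent.** The rise must be under 60 ms, so QTcF < baseline + 60. Together with QTcF ≥ 500, this needs baseline > 440 ms.

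| Period baseline QTcF (ms) | Gap in triplicate-mean QTcF (ms) |
|---|---|
| 440 or less | none |
| 442 | 500 to under 502 |
| 445 | 500 to under 505 |
| 450 | 500 to under 510 |
| 455 | 500 to under 515 |

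The last row is included because the 450 ms limit is an eligibility check. Nothing in 8.3.3 rechecks it against each period's Day 1 baseline, so 510 ms is not a hard ceiling.

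**Step 3: an example.** Baseline 450 ms, QTcF 505 ms, rise 55 ms, so limb (a) does not fire. QT = 505 × (60/70)^(1/3) = 479.7 ms at 70 bpm; at 65 bpm it is 491.7 ms. Limb (b) does not fire at either rate. By contrast, QTcF 509 ms at 61 bpm gives QT 506.2 ms, and limb (b) does fire.

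**Step 4: single tracings.** Limb (a) uses the triplicate mean. A single tracing with QTcF 500 ms at 70 bpm has QT 500 × (60/70)^(1/3) = 475.0 ms. If the mean rise is under 60 ms, that tracing starts no repeats, even from a baseline of 440 ms or less. Section 9.3.1.2 anticipates single tracings of this kind.

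**Step 5: slow rates.** QT 500 ms at 50 bpm is QTcF 500/(60/50)^(1/3) = 470.5 ms. Limb (b) fires, yet QTcF is already below 500 ms, so the release rule can be met while QT has not moved. This is ambiguous rather than plainly wrong, because exclusion criterion 11 and the waiver in 8.3.3 both let QTcF decide.

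**The case against.** The strongest reply is that limb (b) is loose wording for QTcF. The release rule treats the triggering threshold as something QTcF can fall below. The cardiologist rule is judged on QTcF against the same criteria. The waiver calls the prolongation already defined a QTc value, and Appendix 8 sets closely matching limits, both in QTcF. On that reading there is no gap, only a word to correct. This is persuasive as to intent, but it does not settle what staff should do: 8.3.3 names QT and QTcF separately, so a careful reader may take limb (b) at its word.

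The second reply is that other safeguards apply. Section 7.1 is mandatory and covers everything above 500 ms. Section 8.3 allows unscheduled measurements, 8.3.3 calls for further evaluation of clinically significant changes, and Appendix 8 recommends alerts to the investigator and study team. Section 2.3.1 names telemetry, though only in the moxifloxacin row. A reader might therefore infer too much from the gap, namely that such a participant would go unmonitored. The documents do not support that. What stands is narrower: none of these provisions orders the hourly repeats.

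The third reply is rarity, and it stands. The gap in triplicate means needs a high baseline and a rise of roughly 50 to 60 ms, in about 42 healthy participants. Earlier concentration-QT analyses found no significant prolongation (2.2.4), and the maximum mean moxifloxacin change quoted in 4.2 is 7.9 to 11.0 ms.

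**Conclusion.** The concern holds as a minor defect in an operative safety rule. On the literal text, a triplicate-mean QTcF of 500 ms or more starts no mandatory hourly repeats when the period baseline exceeds 440 ms, the rise is under 60 ms, and heart rate exceeds 60 × (QTcF/500)³.

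The size rests on two assumptions. The range of 500 to under 510 ms takes the period baseline at the 450 ms eligibility limit. The absence of a gap at 440 ms or less applies to triplicate means, not to single tracings.

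A reader might infer that every QTcF from 500 to 510 ms above 60 bpm escapes the rule. It does not: the baseline condition is decisive, and 60 bpm is the exact limit only at QTcF 500 ms. Nor do the documents show that uncorrected QT was a deliberate choice. The primary concentration-QTc analysis and the assay-sensitivity test are unaffected.

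**What to change.** In Protocol 8.3.3, change limb (b) to *QT or QTcF of 500 ms or more* in both the hourly-repeat trigger and the 4-hour rule. State that the repeats end, and the 8-hour cardiologist rule is judged, on the interval that triggered. This keeps every present trigger, closes the gap for triplicate means and single tracings, and removes the slow-rate ambiguity.

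Replacing QT by QTcF alone is not recommended. It would drop present triggers at slow rates: for example, QT 520 ms at 50 bpm is QTcF 489.3 ms.

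The cost is a wording change in one protocol section and a few extra ECGs in rare participants. No analysis changes.
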